9.3 Day 14 Telephone Contact

A telephone call will be conducted at 14 ± 4 days from the baseline visit to assess for any changes in status, adverse events, or concomitant medications. Study medication compliance will be discussed, and reminders given about the upcoming confinement visit. If there is an insufficient level of drug compliance (less than 80% overall), the site must consult with the Project Directors and Medical Monitor regarding timing and conduct of the remaining confinement visit procedures. It is possible that subjects will be discontinued early from the study due to insufficient drug compliance.

9.4 Confinement Visit

Admission for the confinement visit should occur 25 ± 2 days following the first dose of study medication. A pre-confinement phone call will be conducted 1-3 days prior to admission and a post-confinement phone follow-up will be conducted approximately 24 hours following discharge. Confinement procedures include functional, cognitive, and behavioral assessments, safety assessments, and review of concurrent medications and adverse events that occur in clinic, blood and CSF collection.

9.4.1 Pre-Confinement Telephone Contact

A telephone call will be conducted at 1-3 days prior to confinement to assess for any changes in status, adverse events, or concomitant medications. Study medication compliance will be discussed, and reminders given about the upcoming confinement visit. If there is an insufficient level of drug compliance (less than 80% overall), the site must consult with the Project Directors and/or Medical Monitor regarding timing and conduct of the Confinement Visit procedures. It is possible that subjects will be discontinued early from the study due to insufficient compliance.

9.4.2 Confinement Visit

The confinement visit will consist of the following: admission procedures, Time 0 blood and CSF sampling, administration of last dose of study drug, 6-hours of blood and CSF sampling, at least a 1-hour observation period while subject remains on bed rest with the observation period

to be extended as clinically necessary as per the Investigator's decision, and discharge procedures. Subjects will be provided with sleeping accommodations during this visit, if necessary, and maybe permitted to remain overnight per investigator discretion in the event there are adverse events associated with the study medications or study procedures.

Subject confinement visit can be split over two (2) consecutive days should the investigator feel that the neuropsychological tests are better completed one day before the lumbar puncture.

Period 1: Admission

Subjects should arrive fasted in the early morning after an overnight fast. Clinical safety labs will be drawn and sent to the central lab for analysis.

Study drug compliance over the preceding days will be assessed. If there is an insufficient level of drug compliance (less than 80% overall), the site must consult with the Project Directors and Medical Monitor) regarding timing and conduct of the remaining confinement visit procedures. It is possible that subjects will be discontinued early from the study due to insufficient study drug compliance.

Admission visit procedures include conducting a Physical and Neurological Exam, administering functional and cognitive evaluations and C-SSRS, collecting vital signs, ECG, clinical labs, reviewing and recording adverse events and concurrent medications.

Period 2: 6-Hour Sampling

If no medical or compliance concerns are identified during the admission procedures, the subject will move on to the 6-Hour Sampling Phase, which entails the following procedures:

1. Place an intravenous line for blood sampling. Alternatively, blood may be sampled by direct venipuncture if deemed appropriate by the PI.
2. Place the CSF catheter.
3. Collect initial samples of blood and CSF (Hour 0).
4. Administer last dose of assigned study drug after the 0 hour sampling.
 - a. Collect CSF (6 mL) and blood (10mL) every hour at the following time points: 1, 2, 3, 4, 5, 6 hours.
 - i. CSF and blood should be taken within \pm 10 mins of hourly times.
 - ii. If unable to obtain a total of 6 mL CSF at any given collection time (e.g. due to participant headache or participant's CSF production level), reduce

the collection volume to a tolerated amount (minimum 2mL). If there is poor flow at any of the time points, then the next collection could be skipped to allow for better flow at the subsequent collection time. For example, if less than 2mL of CSF is collected at the 1-hour time point, then the 2-hour CSF collection could be skipped, and CSF collection would resume at the 3-hour time point.

- b. Perform periodic safety monitoring during the collection period. This includes questions about any symptoms in relation to the CSF catheter (including potential adverse events such as leg or back pain, dizziness or headaches) and vital sign monitoring. Participants also should be asked about pain, redness or swelling at the blood collection site in the arm.
- c. Subjects remain on bed rest throughout the CSF sampling period of 6 hours. They are allowed to use a bedside commode for toileting.

5. After the final 6-hour blood and CSF samples have been collected, remove the blood collection line and LP catheter.
6. Perform final safety monitoring, a physical, and a neurological exam.

The site should complete the LP catheter via their local practice/procedures; however, sites can refer to the LP catheter supporting documentation which will be provided.

If the subject experiences intolerable AE(s) that require early discontinuation of the sampling procedures and removal of the LP catheter, contact the Medical Monitor and Project Directors as soon as possible to discuss the situation. If feasible, the standard 6-hour observation and discharge procedures should be followed to allow for management and follow-up on the adverse events.

Period 3: Observation

The subject should be observed for at least 1 hour following removal of the LP catheter. The subject should remain on bed rest during this 1 hour follow up.

A blood patch will be administered as required if a subject exhibits signs of a post-spinal tap headache that is not managed with bed rest, oral and intravenous fluids, caffeine, and/or mild analgesics (e.g., Ibuprofen, Naproxen or Tylenol). All unused study drug should be returned to the clinical site for final accountability.

Subjects may be permitted to stay overnight in the event there are ongoing adverse events that require monitoring per investigator discretion.

Period 4: Discharge

Prior to discharge, vital signs should be recorded, and a review of AE(s) and Concurrent Medications should be conducted. Upon determination by the investigator (or qualified designee) that the subject is stable, the participant will be discharged. If a participant experiences an unstable AE, please contact the Medical Monitor and Project Directors for guidance on the appropriate course of action to be taken.

9.4.3 Post-Confinement 24-Hour Phone Follow-up

Approximately 24 hours following discharge from the Confinement Visit the subject or a person designated to speak for them will be contacted by phone to confirm the subject's well-being and to query about any new AEs.

10 EARLY TREATMENT/STUDY DISCONTINUATION

The investigators at each site will make every reasonable effort to maximize subject retention. However, if an investigator removes a subject from treatment or study, or if a subject declines further treatment or study participation, an early discontinuation visit will be completed as soon as possible following discontinuation. The early discontinuation visit will contain the same assessments as the confinement (admission) visit. If an in-person visit is not possible, site personnel will complete as much of the early discontinuation visit as possible by telephone.

Subjects who discontinue from the study prior to completing all protocol procedures may be replaced at the discretion of the Coordinating Center, in consultation with the Sponsor.

10.1 Reasons for Early Discontinuation

Participants may withdraw from the study at any time as stated in the informed consent document given to the participant at the time of enrollment. Participants may also be discontinued from treatment/study for reasons such as the following:

- Adverse experience: The participant has experienced an adverse event that, in the opinion of the investigator, requires early termination. This may include abnormal laboratory values.
- Death.
- Safety risk: Any participant who becomes a safety risk to themselves during the trial will be withdrawn.
- Protocol violation: The participant fails to meet protocol entry criteria or does not adhere to protocol requirements.
- Non-compliance: The participant is non-compliant with completion of study-related evaluations and/ or intake of study drugs.
- Development of suicidal or homicidal ideation requiring hospitalization or confinement.
- Consent is withdrawn. The participant wishes to withdraw from the study, or the legally authorized representative wishes that the participant be withdrawn.
- The study is terminated by the Sponsor/Coordinating Center, alone or at the recommendation of the Data Safety Monitoring Board.
- Lost to follow up. Participant could not be recalled back to conduct follow up visits.

11 STUDY-SPECIFIC INSTRUMENTS

We are planning a number of tests that measure states of function, depression, dementia, memory and attention. Those measures include minimally the following:

PD: MMSE, WAIS-IV, MDS-UPDRS

AD: MMSE, WAIS-IV, ADAS-Cog 14, CDR

12 STUDY-SPECIFIC PROCEDURES

12.1 Safety Assessments

Safety will be evaluated by monitoring for changes in the parameters summarized below, including any AEs/SAEs as reported by subjects or observed by the clinical staff, or by the use of concomitant medication during the study.

12.1.1 Physical and Neurological Examination

A medically qualified professional will perform a physical examination that consists of a review of the major body systems (i.e., skin, head/ears/eyes/nose/throat (HEENT), cardiovascular, pulmonary, abdomen, musculoskeletal, and extremities) and a neurological examination which will include an assessment of cranial nerves, strength, coordination, reflexes, sensation, tremor, gait and mental status. Assessments of height, weight, and vital signs (systolic and diastolic blood pressure, pulse, temperature, and respiration) are included.

12.1.2 Electrocardiogram (ECG)

An appropriately qualified individual will conduct a standard 12-lead supine resting ECG. The ECG report must be reviewed, signed, and dated by the site PI (or a medically qualified individual delegated by the site PI). Those with clinically significant ECG findings will be referred for follow-up as deemed appropriate by the investigator and may be excluded from the study.

12.1.3 Clinical Laboratory Evaluations

Blood and urine samples will be obtained for clinical safety lab assessments as described in the Schedule of Events ([Appendix 1](#)). The following table lists the clinical safety lab tests that will be assessed by the central lab at three time points: the screening visit, the pre-confinement visit, and the end of the 6-hour sampling period. Refer to the Laboratory Manual for additional details.

CLINICAL SAFETY LAB TESTS

METABOLIC PANEL	COMPLETE BLOOD COUNT	URINALYSIS
Sodium (Na)	White Blood Cell Count (WBC)	Color
Potassium (K)	Red Blood Cell Count (RBC)	Appearance
Chloride (Cl)	Hemoglobin (Hb)	Specific Gravity
Carbon Dioxide (CO ₂)	Hematocrit (HCT)	pH
Blood Urea Nitrogen (BUN)	Mean Corpuscular Volume (MCV)	Blood
Glucose	Mean Corpuscular Hemoglobin (MCH)	Glucose
Calcium (Ca)	Mean Corpuscular Hemoglobin Concentration (MCHC)	Protein
Creatinine (Crn)	Red Blood Cell Distribution Width (RDW)	Ketones
Bilirubin Total	Mean Platelet Volume (MPV)	Leukocyte Esterase
Albumin	Platelet Count (PLT)	Nitrite
Protein (NOS) Total		Urobilinogen
Glutamic-Oxaloacetic Transferase (AST, SGOT)		Bilirubin
Glutamic-Pyruvate Transferase (ALT, SGPT)		
Alkaline Phosphatase NOS		
COAGULATION PANEL		
PPT/PTT		
[Screening Visit ONLY]		

Lab reports will be reviewed, signed and dated by the site PI (or a medically qualified individual delegated by the PI). If a value is outside of the laboratory's normal range, the clinician will indicate if the value has clinical significance. Those results that are deemed clinically significant may need to be repeated and may require follow up with the subject's primary care physician for further evaluation.

12.2 Biofluids

12.2.1 CSF for Biomarkers

Standard Lumbar Puncture (LP):

A LP will be performed as part of the baseline visit, in the morning (before 10 am is recommended), after an overnight fast.

Participants taking an anti-platelet agent (e.g. Plavix) must be discontinued from that agent for a minimum of 5 days prior to the lumbar puncture. These participants may continue with the agent after a minimum of 24 hours post LP. Participants who are taking anticoagulants (e.g. warfarin (Coumadin) and/or dabigatran (Pradaxa) may not undergo an LP and are not suitable to participate in this study.

Each study participant or a person designated to speak for them will be contacted by phone approximately 24 hours after the LP to confirm participant well-being and any adverse events.

CSF Catheter Sampling:

CSF should be collected at each timepoint during the CSF catheter sampling. At hours 0, 1, 2, 3, 4, 5, 6 (\pm 10min), each 6 mL of CSF is collected.

NOTE: The final dose of study drug should be given **after** the 0 hour sample but **before** the 1 hour sample

NOTE: If unable to obtain a total of 6 mL CSF at any given collection time (e.g. due to participant headache or participant's CSF production level), reduce sampling size and obtain the maximum tolerated amount (minimum 2mL). If unable to obtain a total of 6 mL CSF at any given collection time (e.g. due to participant headache or participant's CSF production level), reduce the collection volume to a tolerated amount (minimum 2mL). If there is poor flow at any of the time points, then the next collection could be skipped to allow for better flow at the subsequent collection time. For example, if less than 2mL of CSF is collected at the 1-hour time point, then the 2-hour CSF collection could be skipped, and CSF collection would resume at the 3-hour time point.

To clear blood associated with needle insertion, the first 1-2 mL (or more if needed) of CSF will be discarded. Refer to the CSF Manual for additional details.

Each study participant or a person designated to speak for them will be contacted by phone one day after being discharged from the confinement visit. The participant will be asked about their wellbeing and the occurrence of any adverse events.

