7.9 Concomitant Medications

7.9.1 Prohibited Concomitant Medications

Current use of anti-coagulants (e.g., warfarin (Coumadin), dabigatran (Pradaxa) or anti-platelet drugs (e.g., Plavix) see section 12.1.1, other than aspirin up to a dose of 325 mg per day, is prohibited. Prospective subjects who in consultation with the prescribing physician can safely discontinue these medications for 4 weeks before screening and remain off these medications throughout the study, can be considered for inclusion in the study.

Use of the following medications is prohibited within 4 weeks of screening and throughout the study:

- tricyclic antidepressants
- antipsychotics prescribed for any reason, except ≤ 50 mg quetiapine daily, risperidone ≤ 1.5 mg/day, olanzapine ≤ 5 mg/day, and aripiprazole ≤ 10 mg/day
- psychostimulants

Investigational agents are prohibited 4 weeks prior to entry and for the duration of the trial.

Initiation of prohibited medications during the course of the study is discouraged, however, if an excluded medication is initiated after screening, the site should consult with the Project Directors and Medical Monitor for further guidance.

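### Protocol section 12.2.1 lets anti-platelet users resume the drug 24 hours after the baseline lumbar puncture, although section 7.9.1 prohibits non-aspirin anti-platelet drugs throughout the study

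*Protocol*

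**What the plan says.** Two protocol sections deal with anti-platelet drugs, and both use Plavix as the example.

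- **Section 7.9.1 (Prohibited Concomitant Medications).** Current use of anticoagulants or anti-platelet drugs, "other than aspirin up to a dose of 325 mg per day, is prohibited". A user may be considered only if, in consultation with the prescriber, the drug can safely be stopped "for 4 weeks before screening and remain off these medications throughout the study". For prohibited drugs begun later, the rule is that "if an excluded medication is initiated after screening, the site should consult with the Project Directors and Medical Monitor for further guidance". The anti-platelet entry carries the pointer "see section 12.1.1".
- **Section 12.2.1 (CSF for Biomarkers), under Standard Lumbar Puncture.** A participant on an anti-platelet agent "must be discontinued from that agent for a minimum of 5 days prior to the lumbar puncture". Such participants "may continue with the agent after a minimum of 24 hours post LP". Anticoagulant users, by contrast, "may not undergo an LP and are not suitable to participate in this study".

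The Standard Lumbar Puncture text describes the baseline procedure. The part of 12.2.1 on CSF catheter sampling states no anti-platelet hold, and neither do the confinement steps in section 9.4.2. Section 12.2.1 also says "Refer to the CSF Manual for additional details"; that manual is not among the documents available.

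**The concern.** The baseline puncture comes just before the first dose, so a restart 24 hours later falls inside the treatment period, where 7.9.1 allows no use. The contrast inside 12.2.1 makes the permission look intended: anticoagulant users are ruled out and anti-platelet users are given a hold-and-resume rule, although 7.9.1 treats the two classes alike.

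The stake is safety at the second spinal procedure. About 25 days after baseline, each participant has a CSF catheter for 6 hours. Section 5.3 lists epidural or subdural bleeding and paralysis among the risks of CSF sampling. A site working from 12.2.1 could bring a participant to that catheter on an anti-platelet drug. A site working from 7.9.1 would not have enrolled a current user, so eligibility could also differ between sites.

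**Working it through.** There is no planned statistical figure to reproduce. The check compares the two rules and then counts days.

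**The rules side by side**

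| Question | Section 7.9.1 | Section 12.2.1 |
|---|---|---|
| May a current user of Plavix take part? | No | Implied yes: called a participant and given a hold |
| Minimum time off before the baseline puncture | 4 weeks before screening, plus the screening interval | 5 days |
| Use between baseline and confinement | None | Allowed from 24 hours after the puncture |
| Hold before the catheter | Not needed, since use is barred | None stated |
| Aspirin up to 325 mg daily | Permitted | Not mentioned; the text says only anti-platelet agent |

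The conflict runs one way. A site that follows 7.9.1 breaks nothing in 12.2.1. A participant who uses the 12.2.1 permission breaks 7.9.1.

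**Does anything else settle it?** The inclusion and exclusion criteria in section 8 do not mention anti-platelet drugs. Section 12.1.1, to which 7.9.1 points, is the physical and neurological examination and contains no such rule; 12.2.1 was probably meant. The aspirin exception does not help, because Plavix is named on both sides.

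**Inputs for the day count.** Day 0 is the baseline puncture and first dose (section 9.2). Earliest resumption is Day 1 (12.2.1). The catheter is on Day 25 ± 2, so Day 23 to 27 (9.4). Screening is 0 to 42 days before baseline (9.1). The first call is on Day 14 ± 4, so Day 10 to 18 (9.3). The pre-confinement call is 1 to 3 days before admission (9.4.1).

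1. Minimum time off before the baseline puncture under 7.9.1: 28 + 0 = 28 to 28 + 42 = 70 days. Under 12.2.1: 5 days.
2. Longest use before the catheter with no catheter hold: 23 − 1 = 22, 25 − 1 = 24, 27 − 1 = 26 days.
3. The same if the phrase about the lumbar puncture is read to include the catheter: 22 − 5 = 17, 24 − 5 = 19, 26 − 5 = 21 days.
4. Use stopped at the Day 14 call: 10 − 1 = 9 to 18 − 1 = 17 days on the drug, then 23 − 18 = 5 to 27 − 10 = 17 days off before the catheter.
5. Use found at the pre-confinement call, Day 23 − 3 = 20 to 27 − 1 = 26: a 5-day hold, if applied, ends on Day 25 to 31.
6. Use found only at admission, Day 23 to 27: a 5-day hold, if applied, ends on Day 28 to 32, beyond the Day 27 limit.

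Items 2 and 3 are ceilings that assume restart on Day 1 and no intervention. Items 5 and 6 apply to the catheter a hold that 12.2.1 does not state for it.

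**The case against.** The strongest reply has four parts.

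*The stricter rule governs.* A site that reads 7.9.1 complies with both sections. That is true, but 12.2.1 gives a written permission with no pointer back to the prohibition, and the supplied text sets no order of precedence.

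*Section 12.2.1 may be the intended special rule.* If the pointer in 7.9.1 was meant for 12.2.1, the prohibition itself would send readers to the hold. This explains why the 5-day hold might exist. It does not reconcile resumption after 24 hours with a requirement to stay off throughout the study.

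*The hold has a legitimate use.* Screening can precede baseline by up to 42 days, and a drug begun in that interval goes to consultation under 7.9.1. A reader might infer that the 12.2.1 text is stray and should simply be deleted. The documents do not support that: it is the protocol's only stated anti-platelet hold before a puncture, and as worded it could also cover permitted aspirin. This part of the objection stands and shapes the fix.

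*Safeguards would intervene.* Medications are reviewed at the Day 14 call, the pre-confinement call and admission. Sampling proceeds only if admission raises no medical concern, and section 9.4.2 leaves catheter placement to local practice, with supporting documentation. These safeguards lower the risk. None states an anti-platelet rule in the protocol text, so a site applying 12.2.1 might see nothing to act on. The CSF Manual and the catheter documentation were not available and may contain a hold.

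**Conclusion.** The inconsistency is real and should be fixed. One section permits what another prohibits, for the same named drug, ahead of a 6-hour spinal catheter. The firm contrast is 5 days off with resumption after 24 hours, against at least 28 days off and no use until the study ends. The possible 22 to 26 days on the drug before the catheter (17 to 21 if a hold is read in) is a conditional maximum, not expected exposure.

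Two stronger readings do not hold. A reader might infer that participants will undergo the catheter while taking these drugs; that requires a site to set aside 7.9.1 and every later check, including local practice, to miss the problem. A reader might also infer that 5 days is unsafe; the documents give no basis for judging that.

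The effect is confined to participant safety and consistent eligibility. The number affected is not given. No endpoint, sample size or analysis changes.

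**What to change.** In section 12.2.1:

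- Delete the sentence allowing resumption after 24 hours.
- State that non-aspirin anti-platelet drugs are prohibited under 7.9.1 until the confinement catheter has been removed and the study is completed.
- Keep the 5-day minimum only as a backstop for use discovered after screening. Apply it to both the baseline puncture and the confinement catheter, with Medical Monitor consultation.
- State whether the backstop covers permitted aspirin.

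In section 7.9.1, replace the reference to 12.1.1 with one to 12.2.1, for this backstop only. The prohibition then stands in 7.9.1 and the two sections do not refer to each other in a circle.

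The cost is wording in two sections, with no new procedure and nobody excluded whom 7.9.1 does not already exclude. One consequence needs a decision: use found at the pre-confinement call may push the catheter past Day 27, and use found at admission always will. The text should say whether the Medical Monitor may then extend the window or should cancel the catheter.
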